### Figure 1. IMPAACT 2036 Overview of Study Design

#### Approximately 90 children overall:

Cohort 1: Up to 70 participants will enroll to achieve at least 50 evaluable. At least 18 evaluable participants will enroll across Weight Bands 1 and 2. At least 32 evaluable participants will enroll in Weight Bands 3, 4, and 5. At least 6 evaluable participants will enroll in Weight Bands 1-4 (each) and at least 10 evaluable participants will enroll in Weight Band 5. Accrual will continue during the interim analyses.

[figure not shown]
Cohort 2: Open to accrual for six months or until the overall study maximum of 90 participants is achieved, whichever occurs first.

Participants who meet criteria for long term safety follow-up will be followed for 48 weeks after their last injection.

Cohort 2 will open following both Cohort 1 interim analyses and Cohort 1 closing to accrual.

with min. n=2 in Weight Band 5

1- LA injection administered :- LA injection administered per Q4W only

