- **Dose-evaluable** The term dose-evaluable refers to participants who will be included in the Week 12 dose-finding interim analyses. Dose-evaluable is defined as participants having been treated on the dose being evaluated, and having either (1) completed all treatment through Cohort 1 Week 12 visit or (2) having experienced any of the following:
  - o study drug-related Grade 3+ events (excluding injection-site adverse events), OR
  - o study drug-related SAE, OR
  - o permanently discontinued from treatment due to study drug-related toxicities (regardless of grade) during the dose-finding period.

Participants who receive oral bridging within the first 12 weeks of their study participation will not be considered dose-evaluable.

- **Evaluable** Evaluable participants will be defined as having either (1) completed all treatment through Cohort 1 Week 24, or (2) having experienced any of the following:
  - o study drug-related Grade 3+ events (excluding injection-site adverse events), OR
  - o study drug-related SAE, OR
  - o permanently discontinued from treatment due to study drug-related toxicities (regardless of grade) during these weeks of treatment.

The two interim analyses will be conducted separately:

- The first interim analysis will be based on Weight Bands 1, 2, and 3 to determine whether criteria have been met to open Weight Bands 4 and 5 to accrual, and to determine if any dosing regimen modifications are indicated. It will be conducted once a minimum of 8 dose-evaluable participants have completed the Week 12 visit, with at least 2 dose-evaluable participants enrolled in Weight Band 3 (20-24.9 kg).
- The second interim analysis will be based on Weight Bands from 3, 4, and 5 to determine if any dosing regimen modifications are indicated. It will be conducted once a minimum of 8 dose-evaluable participants across Weight Bands 3, 4, and 5 have completed the week 12 visit (including any participants in Weight Band 3 who contributed data to the first interim analysis), with at least 2 dose-evaluable participants enrolled in Weight Band 5 (10-13.9 kg).

All available PK, safety, viral load, tolerability, and other relevant data will be reviewed by the CMC.

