## 9.5.2 Safety Guidelines

The Safety Guidelines will consider the adverse event severity, seriousness and attribution to the study drugs. Adverse event attribution to the study drugs will be based on site assessment.

The Safety Guidelines are considered not met, i.e., dose has failed the Safety Guidelines, if:

- at least one participant experienced an adverse event that is fatal or life-threatening and is assessed as related to study drug(s); or
- more than 25% of the participants (e.g., 3 or more of 8 dose-evaluable participants in an interim analysis) experience a Grade 3 or higher adverse event (excluding injection site adverse events, e.g., ISRs) assessed as related to study drug(s) or experience any adverse event assessed as related to study drug(s) that results in permanent discontinuation of the study drug(s).

If none of these conditions are met, then the dose being evaluated has passed the Safety Guidelines.

Given the small sample sizes in a Cohort 1 interim analysis, the information available for safety decisions based on the Safety Guidelines may be imperfect. Two types of sampling errors are possible: 1) if the true rate of toxicity is too high to warrant exposure to the current dose of study drug, the sample data may pass the Safety Guidelines and 2) if the true rate of toxicity is low enough that further exposure to the current dose is warranted, the sample data may fail the Safety Guidelines.

The extent to which the Safety Guidelines protect against the errors described above can be assessed by examining various hypothetical rates of "true toxicity" which could occur if the study drug were used extensively among the participant population at the dose level under question. The hypothetical situations presented in Table 9. (i.e., interim analysis assessment of the Safety Guidelines) range from conditions under which a given dose level would cause a high incidence of severe and life-threatening adverse events to conditions under which severe adverse events would be relatively rare and would not be life-threatening.

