Table 9 uses a multinomial response model to assess the probability of failing the Safety Guidelines under each of these hypothetical situations. The calculations are performed as follows: Each of the eight participants represents a trial, which may have 1 of 3 mutually exclusive outcomes: (i) death or life-threatening adverse event assessed as related to study drug; (ii) a Grade 3 or 4 non-life-threatening adverse event assessed as related to study drug; and (iii) a relatively benign outcome, satisfying neither the criteria in (i) nor (ii).

Table 9.

Probability of Eight Dose-Evaluable Participants Failing Safety Guidelines Under Potential Rates of True Toxicity

True Tox		
Grade 3 or 4 Non-Life Threatening Drug-Related AE	Life Threatening or Fatal Drug- Related AE	Probability of Failing Safety Guidelines
0.50	0.00	0.86
0.50	0.05	0.93
0.50	0.25	1.00
0.25	0.00	0.32
0.25	0.05	0.57
0.25	0.25	0.95
0.05	0.00	0.01
0.05	0.05	0.34
0.05	0.25	0.90
0.00	0.05	0.34
0.00	0.25	0.90

For each of the hypothetical situations above, it is assumed that a sample of eight participants is drawn from the population and that the Safety Guidelines, summarized above, are followed. The probability of failing the Safety Guidelines represents the sum of the probabilities of these sets of results, and "1 minus the probability of failing the Safety Guidelines" represents the probability of passing the guidelines. The "True Toxicity Rates" presented in the table, along with the true rate of having neither of the two types of adverse events represented by the true toxicity rates (which is "1 minus the sum of the true toxicity rates"), provide the probabilities for the outcomes that are used in the multinomial calculations for each of the hypothetical situations.

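### A child with toxicity becomes dose-evaluable at the event and one without only after 12 weeks, so Table 9 understates the chance of failing the interim safety rule as written

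*Protocol*

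**What the plan says.** Section 3.2 fixes who enters the interim: "The term dose-evaluable refers to participants who will be included in the Week 12 dose-finding interim analyses". A child qualifies by "having either (1) completed all treatment through Cohort 1 Week 12 visit or (2) having experienced any of the following"; the listed events are a related Grade 3 or higher event (injection-site events excluded), a related SAE, or permanent discontinuation for related toxicity. The first interim has a floor, not a fixed set: "It will be conducted once a minimum of 8 dose-evaluable participants have completed the Week 12 visit". Some children are removed altogether: "Participants who receive oral bridging within the first 12 weeks of their study participation will not be considered dose-evaluable".

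Figure 1 states: "Accrual will continue during the interim analyses". Section 1.3.3 likewise keeps Weight Bands 1–3 enrolling unless a safety concern arises.

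Section 9.5.2 fails the dose if "at least one participant experienced an adverse event that is fatal or life-threatening and is assessed as related to study drug(s", or if a qualifying related event occurs in "more than 25% of the participants (e.g., 3 or more of 8 dose-evaluable participants in an interim analysis". Its operating characteristics are in Table 9, whose model reads: "Each of the eight participants represents a trial, which may have 1 of 3 mutually exclusive outcomes", with the eight drawn from the population. Section 9.5.4 (scenario 2) pauses accrual for an SMC review if three such events occur before eight dose-evaluable children have accrued.

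**The concern.** The two routes into the set take different times. Between the enrolment of the children who will reach Week 12 and the look itself, further children are dosed. One of these with an early toxicity enters both numerator and denominator. One without toxicity, enrolled on the same day, enters neither. Nothing limits the set to consecutively enrolled children whose 12-week window has elapsed, so the set is selected partly on the outcome it is meant to measure.

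A constructed case shows the mechanism. Suppose 20 children are enrolled, the first 8 complete Week 12 without toxicity, and 3 of the other 12 have an early related Grade 3 event. The fraction is 3/(8+3) = 27%, a failure, although 3/20 = 15% of treated children had toxicity. The case is arranged to make the point; the simulation below measures the average effect.

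At stake is a figure the protocol relies on. Section 9.5.2 names failing an acceptable dose as one of its two errors and quotes 1% for it in a low-toxicity setting. Failing the guidelines bears on opening Weight Bands 4 and 5, and scenario 2 of Section 9.5.4 pauses accrual at once.

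**Working it through.** **Reproducing Table 9.** With g the Grade 3/4 non-life-threatening rate and l the life-threatening or fatal rate, a fixed sample of eight gives

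P(fail) = 1 − Σ(k = 0 to 2) C(8,k) · g^k · (1 − g − l)^(8−k).

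- (0.25, 0): 1 − (0.1001 + 0.2670 + 0.3115) = 0.3215; table 0.32.
- (0.05, 0): 1 − (0.6634 + 0.2793 + 0.0515) = 0.0058; table 0.01.
- (0.05, 0.05): 1 − (0.4305 + 0.1913 + 0.0372) = 0.3410; table 0.34.

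All 11 rows reproduce to two decimals.

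**Inputs for the rule as written.** From the protocol: the two routes, the 12-week window, the minimum of eight, the threshold of more than 25%, and continuing accrual. Not given, so assumed: accrual in the open bands, when toxicities occur, and loss for other reasons. The Schema's 50 evaluable to 70 enrolled children in about 12 months average 50/12 = 4.2 to 70/12 = 5.8 per month, but over all five bands. Only Bands 1–3 are open before the first interim, so slower rates are shown too. Base case: Poisson accrual, toxicity time uniform over 12 weeks, no other loss.

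**Two readings of the trigger.** Reading A looks when the eighth child becomes dose-evaluable. Reading B waits until eight children have passed their own Week 12 date and counts every child dose-evaluable by then. The ranges below run from A to B (at least 40,000 simulated trials per setting; Monte Carlo standard error at most about 0.0025).

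| Accrual per month | 25% rate (Table 9: 0.32) | 5% rate (Table 9: 0.01; exact 0.006) |
|---|---|---|
| 0.5 | 0.36–0.38 | 0.007–0.008 |
| 1 | 0.40–0.43 | about 0.01 |
| 2 | 0.48–0.52 | 0.013–0.015 |
| 4 | 0.63–0.68 | 0.025–0.03 |
| 5.8 | 0.74–0.78 | 0.04–0.05 |

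At a true 25% rate, the mean interim toxicity fraction under A is 0.28, 0.31 and 0.38 at 1, 2 and 4 per month.

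The mixed rows move the same way. At 1, 2 and 4 per month, (0.05, 0.05) goes from 0.34 to 0.39, 0.43 and 0.51–0.52, and (0.25, 0.05) from 0.57 to 0.65–0.66, 0.71–0.74 and 0.82–0.85.

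**Isolating the cause.** Taking the first eight children by enrolment, each with the window elapsed, returns 0.32 and 0.006 at every accrual rate. The admission rule, not the threshold or the arithmetic, produces the difference.

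**Sensitivity (25% rate, 2 per month).** Toxicities confined to weeks 0–4 give 0.59–0.63; confined to weeks 4–12, 0.43–0.46. If an assumed 15% of toxicity-free children leave or receive oral bridging, the result is 0.56–0.59, and even the consecutive-eight set gives 0.40, because those children drop out of the denominator only.

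**The case against.** Section 9.5.2 presents Table 9 as hypothetical situations under a stated sampling assumption, and warns that the information for these decisions may be imperfect. Both points are fair, and the arithmetic is right. But the warning concerns sampling error, and Table 9 is offered as its measure; a systematic upward shift is not disclosed.

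The effect can also be called conservative. In a first study below age 12, counting toxicities promptly is defensible. The CMC reviews all available PK, safety, viral load and tolerability data, and the SMC reviews any dose modification, so the fraction does not decide alone. This stands, and it limits the consequence. It does not make Table 9 describe the rule.

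Accrual in Bands 1–3 is not given, and 5.8 per month is the 70-child maximum averaged over all bands. This also stands: only a range can be shown, and at slow accrual with low toxicity the excess is negligible.

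A reader might infer that an acceptable dose fails several times more often than stated. The documents do not support that as a general claim. At the 25% row the ratio to 0.32 is about 1.1 to 2.1 for 0.5 to 4 per month, and 25% is the rule's own boundary rather than a clearly acceptable rate. At the 5% row, the one the protocol itself treats as low toxicity, the ratio can be large at fast accrual, but only because the base is 0.006; the excess is at most 2 to 3 percentage points up to 4 per month and about 4 points at 5.8.

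**Conclusion.** The point holds as a mismatch between Table 9 and the rule it is meant to describe. Under the dose-evaluable definition as written, the chance of failing was above the fixed-eight figure in every scenario tried. At a 25% true rate it is roughly 0.36 to 0.68 for 0.5 to 4 children per month, and up to 0.78 at 5.8, against 0.32. At a 5% rate it runs from about 0.01 to 0.03 over 0.5 to 4 per month, and to 0.05 at 5.8, against 0.006 exact. The size rests on assumed accrual, toxicity timing and loss. The direction follows from the two admission routes combined with continuing accrual.

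Two stronger inferences should be resisted. The rule does not become more likely to pass a toxic dose; the error is an extra failure, pause or review. And redefining the set as the first eight children by order of first dose would not simply restore Table 9: with 15% toxicity-free loss it gives 0.40 rather than 0.32, and it would alter which events feed a safety pause.

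**What to change.** 1. Recompute Table 9, and the two worked examples that follow it in Section 9.5.2, for the dose-evaluable definition as written. Cover a stated range of accrual rates (including slow ones), toxicity timing and loss for reasons other than toxicity. Keep the fixed-eight figures beside the new ones, labelled as a lower bound across the scenarios computed.
2. At each interim, also show the CMC the toxicity fraction among consecutively enrolled children whose 12-week window has elapsed, and among all treated children.
3. Reconcile Sections 3.2, 9.5.2 and 9.5.4 on which children form the interim set: a minimum of eight, exactly eight, or all who are dose-evaluable at the look, and whether a toxicity case counts towards the eight before its own Week 12 date.

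The 25% threshold, the life-threatening criterion and the pausing triggers are left unchanged. The cost is one recalculated table, a few sentences of wording and two extra lines in the interim report. No additional data are needed.

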#### 3.3 Transition from Step 1 to Step 2: Cohort 1 and Cohort 2a

Eligibility for each Cohort 1 and Cohort 2a participant will be assessed prior to entry into Step 2 and receipt of injectable CAB LA + RPV LA (See Section 4.3 and Section 4.4). The Week 4b visit serves as the Step 2 Entry visit. This visit should be scheduled to occur as soon as possible after Week 4a laboratory test results are available to minimize the time between the Week 4a visit and initiation of the injectable study products. Clinical assessments conducted at the Week 4b visit, and prior to administering the first injection, will also be used to confirm Step 2 eligibility.

Study visits during Step 2 will be scheduled based on the actual Week 4b visit completion date when the first CAB LA + RPV LA injections are administered.

### 3.4 Qualitative Evaluation Design

Qualitative in-depth interviews (IDIs) with a subset of enrolled parents/caregivers will be conducted to complement the quantitative data collected and allow for a mixed-methods approach to evaluate nuanced aspects of acceptability and tolerability, contributing to the secondary objectives of the study. Approximately 30 parents/caregivers will be purposively selected across up to 6 sites for participation in a semi-structured qualitative IDI at Week 24 for Cohort 1 and Cohort 2a and Week 20 for Cohort 2b. Interviews must be completed within the specified interview window but may be conducted as part of a regular study visit or as a stand-alone visit, per site discretion and parent/caregiver preferences. Approximately 18 IDIs will be allocated to Cohort 1 and an additional 12 to Cohort 2. Additional details regarding the qualitative component, including purposive selection criteria and qualitative accrual targets, will be provided in the IMPAACT 2036 study-specific MOP.

Sites selected for the qualitative component will outline procedures for conducting the qualitative component in an IMPAACT 2036 study-specific SOP. Study staff members at each participating qualitative site will conduct the IDIs allocated for their site based on cohort-specific qualitative interview guides that will be developed by the protocol team with input from site staff. Interviews will be conducted in the preferred language of the parent/caregiver, audio-recorded, and then transcribed and translated to English (as needed) for analysis.

#### 4 STUDY POPULATION

This study will be conducted with up to 90 children living with HIV-1 and their parents/caregivers. Children will be selected according to the criteria in Sections 4.1-Section 4.4. Parent/caregiver eligibility criteria are outlined in Section 4.5 and Section 4.6. The study-specific approach to recruitment, screening, and enrollment is described in Sections 4.8 and 4.9.

# 4.1 Inclusion Criteria, Step 1: Entry for Cohort 1, Cohort 2a, and Cohort 2b

Potential participants must meet all of the criteria specified below to be included in this study; in these criteria, "at entry" is used to refer to the day of enrollment in the study:

**4.1.1** Parent or legal guardian is willing and able to provide written permission for child's study participation and, when applicable per institutional review board/ethics committee (IRB/EC) policies and procedures, child is willing and able to provide written assent for study participation.

*Note:* All sites must follow all applicable IRB/EC policies and procedures; for US sites, this includes single IRB (sIRB) policies and procedures.

- **4.1.2** Age two years old to less than 12 years old at entry
- **4.1.3** Body weight  $\geq$ 10 kgs and <40 kgs at entry
- **4.1.4** At entry, willing and able to comply with the study visit schedule and other study requirements, as determined by the site investigator or designee.
- **4.1.5** Confirmed HIV-1-infection based on documented testing of two samples collected from two separate blood collection tubes per Sample #1 and Sample #2 requirements. Test results may be obtained from medical records or from testing performed during the study screening period:
  - For results obtained from medical records, adequate source documentation, including the date of specimen collection, date of testing or date of test result, name of test/assay performed, and test result, must be available in study records prior to study entry. Requirements related to laboratory operations (e.g., Clinical Laboratory Improvements Amendment (CLIA), Good Clinical Laboratory Practice (GCLP), or Virology Quality Assurance Program (VQA)) and related to regulatory authority approvals (e.g., FDA) do not apply to results obtained from medical records.
  - If adequate source documentation is not available, Sample #1 and/or Sample #2 should be collected during the study screening period and tested in the study site's designated testing laboratory. At least one of the tests used to confirm infection must be performed in CLIA-certified or equivalent laboratory (for US sites) or in a DAIDS-monitored laboratory that is GCLP compliant and participates in an approved external quality assurance proficiency testing program (for non-US sites).

For participants with no exposure to breast milk in the past 28 days:

Sample #1 may be tested using any of the following:

- Two rapid antibody-based tests from different manufacturers or based on different principles and epitopes; combination antigen-antibody-based rapid tests may be used.
- One enzyme immunoassay (EIA) OR western blot (WB) OR immunofluorescence assay OR chemiluminescence assay
- One HIV-1 DNA polymerase chain reaction (PCR)
- One quantitative HIV-1 RNA PCR (above the limit of detection of the assay)
- One qualitative HIV-1 RNA PCR
- One HIV-1 total nucleic acid test

Sample #2 may be tested using any of the following:

- Rapid antibody-based test. If this option is used in combination with two rapid antibody-based tests for Sample #1, at least one of the three rapid tests must be FDA-approved and the third rapid test must be from a third manufacturer or based on a third principle or epitope; combination antigen-antibody-based rapid tests may be used.
- One EIA OR WB OR immunofluorescence assay OR chemiluminescence assay
- One HIV-1 DNA PCR
- One quantitative HIV-1 RNA PCR (above the limit of detection of the assay)
- One qualitative HIV-1 RNA PCR
- One HIV-1 total nucleic acid test

For participants with any exposure to breast milk in the past 28 days:

Sample #1 may be tested using any of the following:

- One HIV-1 DNA PCR
- One quantitative HIV-1 RNA PCR (above the limit of detection of the assay)
- One qualitative HIV-1 RNA PCR
- One total HIV-1 nucleic acid test

Sample #2 may be tested using any of the following:

- One HIV-1 DNA PCR
- One quantitative HIV-1 RNA PCR (above the limit of detection of the assay)
- One qualitative HIV-1 RNA PCR
- One total HIV-1 nucleic acid test

All study-specific samples tested to determine HIV-1 status must be whole blood, serum, or plasma. Testing methods and algorithms must be approved for each site by the IMPAACT Laboratory Center (for NIAID-funded sites) or Westat (for NICHD-funded sites). All testing methods should be FDA-approved, if available. On demand nucleic acid-based methods may be acceptable for use in site testing algorithms (for either Sample #1 or Sample #2).

- **4.1.6** Has been on a stable unchanged ART regimen consisting of two or more drugs from two or more antiretroviral drug classes for at least six consecutive months (defined as 180 consecutive days) prior to entry.
- **4.1.7** Has no prior history of switching ART regimens for reasons related to treatment failure based on parent/guardian report and/or available medical records.

*Note:* Participants undergoing dose modifications for growth or who have switched to a new formulation due to toxicity, tolerability, or changes in national treatment guidelines are considered eligible per this inclusion criterion. Treatment failure should be defined by local guidelines.

- **4.1.8** From a specimen collected less than six months (defined as within 179 days) prior to entry, has at least one of the following documented plasma HIV-1 RNA results:
  - <50 copies/mL, or
  - less than the lower limit of detection of the assay

- **4.1.9** From a specimen collected in the 6-18 months (defined as 180 to 545 days) prior to entry, has at least one of the following documented plasma HIV-1 RNA results:
  - <50 copies/mL, or
  - less than the lower limit of detection of the assay
- **4.1.10** At screening, a documented plasma HIV-1 RNA <50 copies/mL.

*Note:* HIV-1 RNA test results at screening cannot be used to satisfy inclusion criterion 4.1.8. If participant does not have a documented HIV-1 RNA test result at screening that satisfies 4.1.8, they should be referred for standard of care testing and return at a later date for screening.

- **4.1.11** Has normal, Grade 1, or Grade 2 results for all the following laboratory tests at screening (i.e., within 28 days prior to entry) based on grading per the Division of AIDS (DAIDS) Table for Grading the Severity of Adult and Pediatric Adverse Events:
  - **4.1.11.1** AST (<5.0 x ULN)
  - **4.1.11.2** ALT (<5.0 x ULN)
  - **4.1.11.3** Total bilirubin (<2.6 x ULN)
  - **4.1.11.4** Lipase (<3 x ULN)
  - **4.1.11.5** Estimated glomerular filtration rate (eGFR; ≥60 ml/min/1.73 m^2)
  - **4.1.11.6** Platelets ( $\ge 50,000 \text{ cells/mm}^3 \text{ or } \ge 50.00 \text{ x } 10^9 \text{ cells/L}$ )
  - **4.1.11.7** Hemoglobin (≥8.5 g/dL or ≥5.25 mmol/L)
  - **4.1.11.8** Neutrophils (≥600 cells/mm³)

*Note:* Laboratory tests may be repeated during the study screening period (i.e., within 28 days prior to entry), with the latest result used for eligibility determination. ALT and total bilirubin should also be assessed in consideration of Section 4.2.7.

- **4.1.12** Has no evidence of chronic hepatitis B infection based on hepatitis B surface antigen (HBsAg), hepatitis B core antibody (HBcAb), and hepatitis B surface antibody (HBsAb) testing at screening; any of the following three combinations of test results are acceptable for inclusion:
  - HBsAg negative, HBcAb negative, HBsAb negative
  - HBsAg negative, HBcAb negative, HBsAb positive
  - HBsAg negative, HBcAb positive, HBsAb positive
- **4.1.13** At screening, has a mean QTc interval (based upon a triplicate reading) less than or equal to 450 msec based on an electrocardiogram (ECG) automated machine readout or calculated using the Fridericia formula.
- **4.1.14** *For participants of childbearing potential*, not pregnant based upon negative blood or urine pregnancy test at entry. Childbearing potential is defined as:
  - Nine years of age or older and having reached menarche or
  - Nine years of age or older, assigned female sex at birth, and engaging in sexual activity (self-reported) that could lead to pregnancy
- **4.1.15** For participants of childbearing potential who are engaging in sexual activity (self-reported) that could lead to pregnancy, at entry, currently using at least one allowable highly effective method of contraception and agrees to use at least one allowable highly

effective method of contraception throughout study participation and for at least 30 days after last oral product use and 48 weeks after last injectable study product use.

Highly effective methods of contraception include:

- Surgical sterilization (i.e., hysterectomy, bilateral oophorectomy, tubal ligation, or salpingectomy)
- Contraceptive intrauterine device or intrauterine system
- Subdermal contraceptive implant
- Progestogen injections
- Combined estrogen and progestogen oral contraceptive pills
- Percutaneous contraceptive patch
- Contraceptive vaginal ring

*Note*: See Section 6.1.3 for details regarding contraceptive counseling. Internal or external condom use is recommended with all other methods of contraception for dual protection against pregnancy and to avoid transmission of HIV-1 and other sexually transmitted infections. Hormonal-based contraceptives must have been initiated within the prescribed time, per the respective contraceptive method, to be considered effective at the time of entry. The site IoR or designee is responsible for ensuring that the contraceptive is used in accordance with the approved product label, and counseling participants on proper use of chosen methods of contraception, including barrier methods.

